5.2 SAMPLE STORAGE, TRACKING AND DISPOSITION

Samples will be ordered in CRIS and tracked through a Clinical Trial Data Management system. Should a CRIS screen not be available, the CRIS downtime procedures will be followed. Samples will not be sent outside NIH without appropriate approvals and/or agreements, if required.

5.2.1 Sample Procedures

Blood and tissue samples, collected for the purpose of research under IRB-approved protocols of the Experimental Transplantation and Immunology Branch and the Immune Deficiency Cellular Therapy Program will be stored and may be archived by the Blood Processing Core (BPC) will be barcoded, with data entered and stored in the Labmatrix utilized by the BPC. This is a secure program, with access to Labmatrix limited to defined [name] lab personnel, who are issued individual user accounts. Installation of Labmatrix is limited to computers specified by [name]. These computers all have a password restricted login screen.

Labmatrix creates a unique barcode ID for every sample and sample box, which cannot be traced back to patients without Labmatrix access. The data recorded for each sample includes the patient ID, name, trial name/protocol number, time drawn, cycle time point, dose, material type, as well as box and freezer location. Patient demographics associated with the clinical center patient number are provided in the system. For each sample, there are notes associated with the processing method (delay in sample processing, storage conditions on the ward, etc.).

Samples are stored in locked freezers at -85°C (sera and plasma) or under liquid nitrogen (cells), according to stability requirements. These freezers are located onsite in the BPC and offsite at NCI Frederick Central Repository Services in Frederick, MD. Visitors to the laboratory are required to be accompanied by laboratory staff at all times. Access to stored clinical samples is restricted. Samples will be stored until requested by a researcher named on the protocol. All requests are monitored and tracked in Labmatrix. All researchers are required to sign a form stating that the samples are only to be used for research purposes associated with this trial (as per the IRB approved protocol) and that any unused samples must be returned to the BPC. It is the responsibility of the NCI Principal Investigator to ensure that the samples requested are being used in a manner consistent with IRB approval.

5.2.1.1 Protocol Completion/Sample Destruction

Once primary research objectives for the protocol are achieved, researchers can request access to remaining samples for human subjects research, providing they have both approval of the Principal Investigator of the original protocol under which the samples or data were collected and either an IRB-approved protocol and patient consent or an OHSRP determination that the activity is exempt from IRB review. Following completion of this study, samples will remain in storage as detailed above. Access to these samples will only be granted following IRB approval of an additional protocol, granting the rights to use the material.

If, at any time, a patient withdraws from the study and does not wish for their existing samples to be utilized, the individual must provide a written request. The PI will record any loss or

unanticipated destruction of samples as a deviation. Reporting will be per the requirements of section **7.2 Error! Reference source not found.**

Sample barcodes are linked to patient demographics and limited clinical information. This information will only be provided to investigators listed on this protocol, via registered use of the Labmatrix. It is critical that the sample remains linked to patient information such as race, age, dates of diagnosis and death, and histological information about the tumor, in order to correlate genotype with these variables.

6 DATA COLLECTION AND EVALUATION

6.1 DATA COLLECTION

Data will be prospectively collected and entered into an NCI 21 CFR Part 11-compliant data capture system using pre-designed CRFs. All persons must have signed an Informed Consent and have an on-study confirmation of eligibility form completed before entering on the study. Complete records will be maintained on each patient including the hospital chart with any supplementary information obtained from outside laboratories, radiology reports, or physician's records. These records will be the primary source documents that form the basis for the research record. The primary source documentation will assure the availability of the following: on-study information, including patient eligibility data and patient history; flow sheets, specialty forms for pathology, radiation, or surgery; and off-study summary sheet, including a final assessment by the treating physician.

The PI will be responsible for overseeing entry of data into a 21 CFR Part 11-compliant data capture system provided by the NCI CCR and ensuring data accuracy, consistency and timeliness. The principal investigator, associate investigators/research nurses and/or a contracted data manager will assist with the data management efforts. Primary and final analyzed data will have identifiers so that research data can be attributed to an individual human subject participant.

All adverse events, including clinically significant abnormal findings on laboratory evaluations, regardless of severity, will be followed until return to baseline or stabilization of event.

Document AEs from the first study intervention, Study Day 1, through 30. Beyond 30 days after the last intervention, only adverse events which are serious and related to the study intervention need to be recorded.

An abnormal laboratory value will be considered an AE if the laboratory abnormality is characterized by any of the following:

- Results in discontinuation from the study
- Is associated with clinical signs or symptoms
- Requires treatment or any other therapeutic intervention
- Is associated with death or another serious adverse event, including hospitalization.
- Is judged by the Investigator to be of significant clinical impact
- If any abnormal laboratory result is considered clinically significant, the investigator will provide details about the action taken with respect to the test drug and about the patient's outcome.

End of study procedures: Data will be stored according to HHS, FDA regulations and NIH Intramural Records Retention Schedule as applicable.

Loss or destruction of data: Should we become aware that a major breach in our plan to protect subject confidentiality and trial data has occurred, this will be reported expeditiously per requirements in section **7.2.1**.

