Neutrophils $< 1.0 \times 10^9/L$, platelets $< 50 \times 10^9/L$, creatinine ≥ 1.5 times the upper limit of normal **or** estimated creatinine clearance $< 50 \text{ mL/min/1.73m}^2$ (Cockcroft-Gault formula), serum aspartate aminotransferase or alanine aminotransferase concentration $> 3 \times \text{ULN}$ or total bilirubin $\geq 1.5 \times \text{ULN}$

Progressive malignancy, uncontrolled infection or any major organ dysfunction as defined by the protocol

Design:

This is a Phase 1/2 trial to determine the safety and efficacy of baricitinib in patients with cGVHD that is refractory to steroids.

Patients will initially be treated with baricitinib at 2mg daily for 12 weeks. If the response at 12 weeks is a CR and there has not been a DLT, the dose will remain at 2mg daily for an additional 12 weeks, with the primary response assessment at 24 weeks of total treatment. If the response is a PR or stable disease, the dose will be increased to 4mg daily for an additional 12 weeks, with the primary response assessment at 24 weeks of total treatment. If there is progression of disease at any time within the first 12 weeks, the dose can be increased to 4mg daily at that time, and patients will continue for a total of 24 weeks of treatment. Patients will have the option to continue baricitinib for an additional 6 months as tolerated if they have stable or responding disease.

The co-primary endpoint of safety will be determined by rate, severity, and duration of adverse events based on CTCAE v4 criteria. Assessment for DLTs will occur every 2 weeks during the first 4 weeks of each dose level. Safety monitoring will occur every 4 weeks thereafter.

The co-primary endpoint of efficacy will be defined as rate of overall response at 24 weeks per NIH consensus criteria (CR or PR).

Peripheral blood samples will be collected prior to treatment, at 2 weeks, at 12 weeks and every 12 weeks thereafter to evaluate cytokine and cellular profiles, STAT phosphorylation, candidate chronic GVHD biomarkers. Pharmacokinetic studies will also be performed at each dose level.

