1.2.3 Baricitinib

Baricitinib (LY3009104, formerly INCB028050, Eli Lilly and Company) is a selective JAK1/2 inhibitor that has been studied in patients with inflammatory conditions such as rheumatoid arthritis, psoriasis, and diabetic nephropathy. It is an oral, potent, and reversible inhibitor of JAK1 (IC₅₀=5.9 nM) and JAK2 (IC₅₀=5.7 nM), with less potency for JAK3, tyrosine kinase 2 (TYK2), or other kinases.⁴⁵ In addition, it has demonstrated excellent potency for inhibition of IL-2-, IL-6-, and IL-23- stimulated phosphorylation of JAKs and STATs, and IL-2 induced proliferation of T-cells. In preclinical models of arthritis, it has demonstrated anti-inflammatory effects while preserving humoral immunity and had no hematologic effects.⁴⁵ It has been tested in doses of 0.5mg-20mg in over 3000 patients and healthy volunteers, and the safety profile is well understood.^{46,47} Phase 1, 2, and 3 studies in RA have been completed, and several studies in patients with psoriasis and diabetic nephropathy are ongoing. Common toxicities seen across studies include decreases in hemoglobin and neutrophils (mean values usually remaining within the normal range), increases in platelets (mean values usually remaining within the normal range), increases in creatinine (mean values usually remaining within the normal range) and increases in exposure in patients with renal impairment, increases in total cholesterol, high-density lipoprotein (HDL), low-density lipoprotein (LDL), and triglycerides, increases in hepatic enzymes, increases in creatine phosphokinase (CPK), and increased incidence of infections (mostly respiratory). Decreases in neutrophils and hemoglobin and other lab abnormalities have been reversible upon discontinuation of the drug.

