3.1.1 Dose Limiting Toxicity

DLT will be defined as any grade ≥ 3 non-hematologic or grade ≥ 4 hematologic adverse event, or hemoglobin < 6.5 g/dL, within 4 weeks of starting any dose level (1mg, 2mg or 4mg) except those that are clearly and incontrovertibly due to extraneous causes. One inpatient dose de-escalation after a DLT will be permitted in patients who have not experienced cGVHD progression. In patients that have experienced disease progression, further dosing will cease in a patient at the occurrence of the first DLT.

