8 SPONSOR PROTOCOL/SAFETY REPORTING

8.1 DEFINITIONS

8.1.1 Adverse Event

Any untoward medical occurrence in a patient or clinical investigation subject administered a pharmaceutical product and which does not necessarily have a causal relationship with this treatment. An adverse event (AE) can therefore be any unfavorable and unintended sign (including an abnormal laboratory finding), symptom, or disease temporally associated with the use of a medicinal (investigational) product, whether or not related to the medicinal (investigational) product (ICH E6 (R2))

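### Section 6.1 decides when a laboratory value is an adverse event without using CTCAE grade, so silent high-grade values can drop out of the co-primary safety rate and the DLT count

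*Combined protocol and SAP*

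**What the plan says.** Section 6.1 states: "An abnormal laboratory value will be considered an AE if the laboratory abnormality is characterized by any of the following". The first condition is "Results in discontinuation from the study". The next three are clinical signs or symptoms, a need for treatment, and association with death or another serious event. The fifth is "Is judged by the Investigator to be of significant clinical impact". The list names no CTCAE grade and no interruption or reduction of study drug.

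Other sections rely on grade:
- Précis, Design: "The co-primary endpoint of safety will be determined by rate, severity, and duration of adverse events based on CTCAE v4 criteria".
- Section 3.1.1: "DLT will be defined as any grade ≥ 3 non-hematologic or grade ≥ 4 hematologic adverse event, or hemoglobin < 6.5 g/dL", within four weeks of starting a dose level and not clearly due to an extraneous cause.
- Section 3.3: dose holds and reductions follow the grade of toxicity, defined there as events at least possibly related to baricitinib.

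Section 8.1.1 gives the general definition, under which an AE can be "any unfavorable and unintended sign (including an abnormal laboratory finding". Section 6.1.2 drops grade 1 events, and Appendix H collects AEs of grade 2 or higher. Appendix H also collects the protocol's laboratory results as a separate item. Section 10 has no safety analysis beyond the rule that stops use of a dose level once two-thirds of its patients have a DLT requiring dose reduction or discontinuation.

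**The concern.** Section 1.2.3 lists the drug's common toxicities, and most are laboratory findings: hemoglobin, neutrophils, platelets, creatinine, lipids, hepatic enzymes and CPK. It also says that baricitinib has not been evaluated in GVHD, so measuring these effects in this population is part of the co-primary aim.

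If a laboratory value enters the AE record through a list that ignores grade, a high-grade value with no symptoms and no treatment has one route in: the investigator's opinion that it matters clinically. The trial has a single treatment arm at a time, and under 7.4.1 the research team and principal investigator review the events. Two staff members following the same protocol could classify the same value differently. At stake are the completeness of the co-primary AE rate and the consistency of the DLT count that feeds the safety stopping rule.

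**Working it through.** **Step 1. Follow one value through the text.** Take a grade 3 CK or transaminase rise, or a grade 4 neutrophil count, at C1D15, in a patient with no symptoms, no treatment for it and no serious event. The study calendar draws CBC and serum chemistry at that visit, and its footnote on chemistry includes CK, AST and ALT.

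| Section | What it uses | Result for this value |
|---|---|---|
| 6.1 | Five conditions, no grade | AE if judged of significant clinical impact; otherwise no listed condition is met |
| 8.1.1 | Unfavorable, unintended sign; laboratory findings included | Can be an AE without that judgement |
| 3.1.1 | Grade of an adverse event | DLT only if first accepted as an AE |
| 3.3 | Grade of related toxicity | Does not refer to the 6.1 list |
| Précis | Rate, severity and duration of AEs | Counted only if accepted as an AE |

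The sections do not agree on the status of this value. Hemoglobin differs: below 6.5 g/dL it is a DLT in its own right under 3.1.1. No other laboratory test has a stand-alone threshold there.

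**Step 2. Check which tests can be affected in the DLT window.** CBC and chemistry are drawn at C1D15 and C2D1, and again at C4D15 and C5D1 after an escalation at week 12. The fasting lipid panel is drawn at screening and baseline and then not until week 12, followed by weeks 24, 36 and 48 and off treatment. Lipids therefore bear on the co-primary AE rate. They are not scheduled within the first four weeks of treatment, nor between weeks 12 and 24.

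**Step 3. Size.** The documents state no DLT rate and no share of events recorded, so there is no figure to reproduce. The following is an illustration only. Let q be the true proportion of patients with a qualifying DLT and c the share of those recorded. The chance that recorded DLTs reach two-thirds of n patients is P(X ≥ k), with X ~ Binomial(n, q·c) and k the smallest integer at or above 2n/3. For n = 7, 2 × 7/3 = 4.67, so k = 5.

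| Assumed q (n = 7, k = 5) | c = 1 | c = 0.90 | c = 0.75 | c = 0.50 |
|---|---|---|---|---|
| 0.33 | 0.043 | 0.028 | 0.012 | 0.002 |
| 0.50 | 0.227 | 0.153 | 0.074 | 0.013 |
| 0.67 | 0.578 | 0.426 | 0.231 | 0.046 |
| 0.80 | 0.852 | 0.692 | 0.420 | 0.096 |

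At q = 0.67 the same four values of c give 0.745, 0.652, 0.504 and 0.261 for n = 3 (k = 2), and 0.613, 0.360, 0.099 and 0.002 for n = 21 (k = 14).

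Here c covers all DLTs, not only laboratory ones. If a share L of DLTs is laboratory-only and a share s of those is recorded, c = 1 − L(1 − s). With L = 0.5 and s = 0.5, c = 1 − 0.5 × 0.5 = 0.75.

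**The case against.** **The wording is "if" and not "only if".** This stands. Section 6.1 can be read as operational examples under the general definition in 8.1.1, and 8.2 refers to 6.1 only for the time frame of recording. A reader might infer that 6.1 strictly excludes everything else, but the text does not say so. On the permissive reading, however, the protocol has no rule for when a laboratory value without those features is an AE, and the inconsistency remains.

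**Appendix H and 3.3 do not carry the weight a reader might put on them.** This also stands. Appendix H sets which AEs are collected; it does not turn every grade 2 laboratory value into an AE. Section 3.3 acts on the grade of related toxicity without using the 6.1 list, so it cannot be said that 6.1 switches off the dose-modification rules.

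**Investigators will often catch these values.** Probably so. DLTs are assessed every two weeks in the window, the team discusses each patient weekly, and a value that changed dosing would probably be judged significant. Section 1.2.3 adds that mean hemoglobin, neutrophil, platelet and creatinine values usually stayed in the normal range and that laboratory abnormalities were reversible. DLT-grade values may be uncommon.

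**The data are not lost.** Correct: Appendix H captures the results, so grades can be derived later. But the plan does not say that this will be done.

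**No decision is shown to change.** One reclassified patient moves an observed rate by 1/7 = 14.3 or 1/21 = 4.8 percentage points. A reader might take that as evidence of harm, but it is arithmetic that fits any misclassified event. The stopping rule also counts only DLTs that require dose reduction or discontinuation.

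**Conclusion.** The point holds as a possible under-count with a cheap remedy. Section 6.1 gives a stated rule that omits grade, while the co-primary endpoint and the DLT definition depend on graded adverse events. For an asymptomatic, untreated, non-serious high-grade CK, transaminase or neutrophil value, undefined judgement decides whether it counts.

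The documents do not support the stronger conclusion that laboratory toxicity will be missed, or that the DLT count will be wrong. The size is unknown. The probabilities above rest on assumed true DLT rates of 0.33 to 0.80 and assumed recording of 50% to 100%, on reading the stopping rule as a proportion applied at the given n, and on every counted DLT requiring dose reduction or discontinuation. They show that the stopping rule is sensitive to incomplete recording, not that recording will be incomplete.

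**What to change.** **Analysis.** Alongside the co-primary AE rates, report for every scheduled laboratory test each patient's worst post-baseline CTCAE v4 grade, tabulated against baseline grade. Derive the grades from the results already collected under Appendix H, at the visits where each test is drawn. For lipids that means baseline, week 12 and later. This table does not depend on whether a value was recorded as an AE.

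**Text.** The sponsor must reconcile 6.1 with 8.1.1, 3.1.1 and 3.3 so that the same laboratory value is classified the same way in each. Which values count as DLTs, and how they are managed, is for the sponsor to decide.

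**Cost.** A little more analysis work and no new samples or visits. Reported laboratory toxicity rates may be somewhat higher than under the present text.

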6.1.1 Eligibility Checklist

The eligibility checklist is to be completed at study entry by the protocol research nurse who will forward the checklist to the Central Registration Office.

6.1.2 Adverse Events

Grade 1 adverse events will not be collected on this protocol.

6.2 DATA SHARING PLANS

6.2.1 Human Data Sharing Plan

What data will be shared?

I will share human data generated in this research for future research as follows (check all that apply):

De-identified data in an NIH-funded or approved public repository.

De-identified data in BTRIS (automatic for activities in the Clinical Center)

De-identified or identified data with approved outside collaborators under appropriate agreements.

How and where will the data be shared?

Data will be shared through (check all that apply):

An NIH-funded or approved public repository. Insert name or names: clinicaltrials.gov.

BTRIS (automatic for activities in the Clinical Center)

Approved outside collaborators under appropriate individual agreements.

Publication and/or public presentations.

When will the data be shared? (check all that apply)

Before publication.

At the time of publication or shortly thereafter.

6.2.2 Genomic Data Sharing Plan

Not applicable. No genomic data, large scale or otherwise, is generated on this study.

6.3 RESPONSE CRITERIA

6.3.1 Definitions

Evaluable for toxicity: All patients will be evaluable for toxicity from the time of their first treatment with baricitinib.

Evaluable for efficacy: Patients who complete 6 months of therapy will be evaluable for the primary endpoint of efficacy assessment. Patients who progress earlier will be also included in

the analysis of efficacy. Patients should have received at minimum of 75% of planned baricitinib doses to be evaluable for the primary efficacy 6 month endpoint.

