6.3.2.1 Response Criteria

Efficacy will be assessed using NIH consensus criteria measuring for therapeutic response in clinical trials for cGVHD.

- **CR** is defined as resolution of all manifestations in each organ or site
- **PR** is defined as improvement at least 1 organ or site without progression in any other organ or site. The criteria for PR and progression are provided in [Appendix K](#)
- **Lack of Response:** including unchanged, mixed response, and disease progression:
- **Mixed response:** CR or PR in at least 1 organ accompanied by progression in another organ
- **Disease progression:** see [Appendix K](#) for organ criteria
- **Unchanged:** Outcomes that do not meet the criteria for CR, PR, disease progression, or mixed response

As outlined in Section [3.7](#), type of involved organ, location and its measurements will be recorded at scheduled evaluations and reported on the appropriate CRF, equal to “Chronic GVHD Assessment (Clinician) Form,” ([Appendix F](#)). All other measurements not being included in primary assessment but clinically related to cGVHD (e.g., change of pigmentation) will be reported in the source documents.

Skin and skin appendages: Skin assessment will be based on the NIH 0-3 Skin Score, which correlates with cGVHD severity, symptoms, and survival ([Appendix D](#)). Clinician-perceived severity of sclerosis will also be captured on a 0-10 scale. Patient-reported symptoms will be captured on a 0-10 scale and on the Lee symptom scale.

Musculoskeletal connective tissue: Assessment of joint range of motion will be performed by the photographic range of motion (P-ROM) scale and the NIH 0-3 Joint Score, which correlate with changes in joint involvement. In a prior study, both scales performed well but the Joint/Fascia scale better reflected clinical perception of improvement, and the P-ROM better reflected the clinical perception of worsening³³. If these measurements are discrepant, priority

will be given to the NIH 0-3 scale when improvement is detected, and to P-ROM when worsening is detected. If the resolution cannot be achieved then the priority will be given to the NIH 0-3 Joint/Fascia scale, as the P-ROM is of more recent origin and still deemed exploratory in the 2014 NIH cGVHD organ staging recommendations⁴.

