10 STATISTICAL CONSIDERATIONS

The primary objectives of the study are to determine the tolerability and efficacy of baricitinib in patients with steroid-refractory cGVHD. The primary efficacy objective is to treat a total of 21 patients in either cohort 1 or cohort 2 in order to have 80% power to detect a response rate consistent with 30% and ruling out 10%, with a one-sided significance level of 0.10.

Patients will first be enrolled onto cohort 1, and in an initial futility analysis, if 0 of the first 7 patients enrolled in cohort 1 have responded, then subsequent patients will be accrued to cohort 2, starting treatment at the higher dose (4mg daily). If 1 or more of the initial 7 patients treated in cohort 1 has a response, then a total of 21 evaluable patients will be treated in cohort 1.

If patients are enrolled onto cohort 2, and if 0 of the first 7 patients enrolled in cohort 2 have responded, then no further patients will be accrued onto the trial. On the other hand, if 1 or more of the initial 7 evaluable patients enrolled in cohort 2 have responded then a total of 21 evaluable patients will be treated in cohort 2.

As an early stopping rule for safety, if 2/3 or greater patients at any given dose level experiences a dose limiting toxicity requiring dose reduction or discontinuation, that dose will not be subsequently used. Accrual will continue at a lower dose level with no further dose escalation, unless this occurs at the lowest dose level, at which time accrual to the study will be stopped.

If patients are enrolled in both cohort 1 and cohort 2, then up to 28 evaluable patients may be required (either 21 in cohort 1 or 7 in cohort 1 and 21 in cohort 2). In order to allow for a small number of inevaluable patients, the accrual ceiling will be set at 31. It is anticipated that 8-12 patients may be enrolled onto this protocol per year; thus, 2 to 4 years may be required to accrue up to 31 patients.

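### The primary week-24 response rate leaves out treated patients who stop without cGVHD progression, and no all-treated rate is planned beside it

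*Combined protocol and SAP*

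**What the plan says.** Section 6.3.1 defines who counts for efficacy in three sentences. The base rule is "Patients who complete 6 months of therapy will be evaluable for the primary endpoint of efficacy assessment". Early failures are added: "Patients who progress earlier will be also included in" the efficacy analysis. A dose condition follows: "Patients should have received at minimum of 75% of planned baricitinib doses to be evaluable for the primary efficacy 6 month endpoint". For safety, the same section takes everyone: "All patients will be evaluable for toxicity from the time of their first treatment with baricitinib".

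Sections 3.1, 3.3 and 3.9.1 provide several ways off treatment that are not cGVHD progression: a further DLT at the reduced dose, grade 4 non-hematologic or infectious toxicity, an interruption beyond 28 days, and the patient's own request. Sections 6.3.2, 6.3.2.1 and 10 do not say how such a patient counts at week 24. Section 6.3.2.1 describes lack of response as "including unchanged, mixed response, and disease progression". Section 8.4 treats death from disease progression as captured by the response endpoint, but nothing comparable is said of other deaths.

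Section 10 tests 30% against 10% at a one-sided level of 0.10 with 80% power. If at least one of the first seven patients responds, "then a total of 21 evaluable patients will be treated in cohort 1"; cohort 2 follows the same rule. On accrual it says: "In order to allow for a small number of inevaluable patients, the accrual ceiling will be set at 31". It states no success cut-off, no confidence interval, and no rule for a missing week-24 assessment. Section 6.3.2.2 adds 12-week response and overall survival as secondary assessments. Neither is a week-24 response rate in all treated patients.

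**The concern.** Completing six months and taking 75% of doses are both events after baseline, and both depend on tolerability. A patient who leaves for toxicity in month two, without progression, meets neither route into the efficacy set. That patient is left out of the denominator, and accrual to 21 evaluable patients can fill the place.

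The resulting rate describes patients who stayed on baricitinib or progressed on it. The question a reader will usually bring is what share of patients started on the drug were in response at week 24. The two rates agree if those who stopped would have responded as often as the rest. The evaluable rate is too high to the extent that they had not responded. Efficacy is a co-primary endpoint with a formal test against 10%, so the effect on that test has to be checked as well as the effect on the reported percentage.

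**Working it through.** **Inputs.** From Section 10: null rate 10%, target 30%, one-sided level 0.10, power 80%, 21 evaluable patients, at most 28 evaluable over both cohorts, ceiling 31. The documents give no stopping rate, so the number dropped is an assumption and is shown as a range.

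**1. Reproduce the plan's figure.** Exact single-stage binomial, P(X ≥ r | n = 21):

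| Cut-off r | Level at 10% | Power at 30% |
|---|---|---|
| 4 | 0.152 | 0.914 |
| 5 | 0.052 | 0.802 |
| 6 | 0.014 | 0.637 |

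Five of 21 is the smallest count with a level of at most 0.10, and its power matches the stated 80%. The cut-off of 5 is therefore inferred. This calculation ignores the 12-week look.

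**2. Room for dropped patients.**
- Cohort-2 path: 31 − 7 − 21 = 3.
- Cohort-1 path: 31 − 21 = 10. Seven of these places exist because the ceiling also has to cover the two-cohort path. The margin meant for inevaluable patients is 31 − 28 = 3.

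**3. Restore k dropped patients as non-responders.** The rate becomes x/(21 + k), with p = P(X ≥ x | 21 + k, 0.10):

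| Responders / treated | Rate | One-sided p | One-sided 90% lower bound |
|---|---|---|---|
| 5/21 (k = 0) | 23.8% | 0.052 | 12.1% |
| 5/24 (k = 3) | 20.8% | 0.085 | 10.5% |
| 5/25 (k = 4) | 20.0% | 0.098 | 10.1% |
| 5/26 (k = 5) | 19.2% | 0.112 | 9.7% |
| 6/31 (k = 10) | 19.4% | 0.083 | 10.5% |

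With 5 responders the conclusion holds up to k = 4 and fails at k = 5. With 6 it holds even at the full ceiling. A reversal therefore needs exactly 5 responders and at least 5 dropped, which step 2 allows only on the cohort-1 path.

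**4. If the dropped patients are not all non-responders.** If 1 of 3 had responded, the rate would be 6/24 = 25.0%, above 23.8%. The size and the sign of the bias depend on their response.

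**5. How likely is a reversal?** Assume the cohort-1 path, a 30% response rate in evaluable patients, stopping independent of response, and no effect of the 12-week look. Then P(reversal) = P(exactly 5 of 21) × P(5 to 10 dropped before 21 are evaluable, negative binomial), with the first factor 0.1643:
- 5% stopping: 0.1643 × 0.0072 = 0.0012
- 10% stopping: 0.1643 × 0.0979 = 0.016
- 20% stopping: 0.1643 × 0.5466 = 0.090

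The three stopping rates are assumptions.

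**6. The 75% rule.** If planned doses means 24 × 7 = 168 daily doses, 75% is 126, and a completer fails only with more than 42 missed. A single 28-day hold (28/168 = 16.7%) does not exclude anyone. But a patient taken off treatment for progression at week 10, for example, has had at most 70/168 = 41.7% of those doses. Read literally, the dose sentence would remove a patient whom the preceding sentence includes. If planned doses means doses due up to the stop, the same patient can have 70/70.

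**The case against.** The strongest reply is that an evaluable set for activity, with tolerability judged separately in all treated patients, is a recognisable phase 1/2 choice. The most obvious failures, early progressors, are kept in. Those who stop count in the co-primary safety endpoint. At the plan's own margin of 3 the decision does not change. All of this stands, and it limits the point to adding an analysis.

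It might also be said that the unchanged category in 6.3.2.1 catches everyone else. That category classifies a patient who has been assessed. It does not set the denominator, which 6.3.1 does.

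Four stronger readings are tempting and should not be drawn:
- *The all-treated rate could not be known.* Appendix H collects response at each timepoint and the date and reason for stopping treatment, so the rate can be recovered. It is only not planned.
- *The type I error is inflated.* The Précis and Section 10 attach 10% to 21 evaluable patients, and on that reading the level is 0.052. It passes 0.10 only if 10% is taken as an all-treated rate, every dropped patient is a non-responder, and more than about 17% drop. With 5 of 26 dropped, for instance, the evaluable rate is 0.10/(21/26) = 0.124 and P(X ≥ 5 of 21) = 0.109.
- *The futility look uses a conflicting denominator.* Section 10 says "if 0 of the first 7 patients enrolled in cohort 1 have responded, then subsequent patients will be accrued to cohort 2", but it and Section 3.1 also speak loosely of treated and evaluable patients. The look is on 12-week response, so a six-month set could not apply to it.
- *The all-treated rate should become primary, with a cut-off that moves with N.* That is a redesign. The exact cut-off rises from 5 to 6 at N = 26. If 30% describes evaluable patients, the all-treated rate is 0.30 × 21/26 = 24.2% or 0.30 × 21/31 = 20.3%, and power falls to 63% at N = 26 and 62% at N = 31.

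**Conclusion.** The point holds as a gap in the planned analysis. Under 6.3.1, treated patients who stop without cGVHD progression are neither in the week-24 denominator nor counted as non-responders, and no other section returns them. The primary rate is conditional on staying on treatment.

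At the inferred cut-off, restoring 3 non-responders lowers the reported rate by 3.0 percentage points (23.8% to 20.8%) without changing the conclusion. A reversal is confined to exactly 5 responders with 5 or more dropped on the cohort-1 path. These figures rest on the inferred cut-off of 5, on replacement being implied by the accrual wording, and on the worst case that every dropped patient is a non-responder. The stated sample size is not in error. The value of the change lies mainly in the reported rate, with little bearing on the test.

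**What to change.** In 6.3.1 and Section 10, prespecify a second week-24 response rate, reported alongside the evaluable rate:

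- **Population:** all patients in the cohort who received at least one dose, the set 6.3.1 already uses for toxicity.
- **Non-responder:** anyone without a documented week-24 CR or PR, or who started new systemic cGVHD therapy before week 24. Steroid pulses allowed by Section 4.1 are not new therapy.
- **Estimate:** the proportion with its exact confidence interval. For illustration, the exact 95% interval is 8.2% to 47.2% for 5/21 and 7.1% to 42.2% for 5/24.

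In 6.3.1, also state that the 75% rule does not exclude early progressors, and define planned doses.

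The cost is wording and one extra analysis. No new data are needed: non-response follows from the absence of a documented week-24 response, and 6.3.2.3 already records the need for secondary systemic therapy. The all-treated rate will usually be the lower of the two, and it counts a patient who was responding when treatment stopped as a failure, which is a reason to show both. The evaluable rate stays primary, so design and power do not change.
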